This cross-over study aims to investigate the impact of two metabolically distinct diets on Glycated hemoglobin, cardiovascular health, the gut microbiome, and metabolic status. Participants are recruited using media advertisements, email lists, and clinician referral ([name]) from previous recruitment for nutrition studies conducted by our laboratory group. Forty participants are planned to be randomized between the two arms: (1) start with 12 week WFKD and switch to 12 week Med-Plus; (2) start with 12 week Med-Plus and switch to 12 week WFKD. Randomization will be stratified by diabetes vs pre-diabetes status. As displayed in figure above, clinical and metabolic measurements are taken at baseline, and weeks 0, 6, 12, (Phase I, weeks 1-12), 18, 24 (Phase II, weeks 13-24) and 36 (Maintenance Phase). Continuous glucose monitoring will be collected five times during the trial, each time data will be collected every hour for ten days.

Primary Outcome:

• Difference in percent difference from baseline after 12 weeks of each phase

Secondary Outcomes:

- Difference in percent difference from baseline in LDL cholesterol after 12 weeks of each phase
- Difference in percent difference from baseline in HDL cholesterol after 12 weeks of each phase
- Difference in percent difference from baseline in triglycerides after 12 weeks of each phase
- Difference in percent difference from baseline in fasting insulin after 12 weeks of each phase
- Difference in percent difference from baseline in blood pressure after 12 weeks of each phase
- Difference in percent difference from baseline in weight after 12 weeks of each phase
- Difference in percent difference from baseline in alpha diversity after 12 weeks of each phase. Primary metric of alpha diversity will be using number of observed sequence variants ("species") determined by standard 16S rRNA amplicon sequencing (V3-V5 region followed by DADA2 to define error-corrected sequence variants). *Note: Higher alpha diversity is better. The units are the # of sequence variants*
- Difference in percent difference from baseline in composite of short-chain fatty acids (SCFA) concentration (ug/g stool: acetate + propionate + butyrate) after 12 weeks of each phase

Exploratory outcomes:

- Difference in satisfaction with WFKD and Med-Plus diets, using a 5-point Likert scale (1=not at all satisfied; 2=slightly satisfied; 3=moderately satisfied; 4=very satisfied; 5=extremely satisfied).

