- Difference in adherence to diet protocols by diabetes vs. pre-diabetes status, according to 3day food records.
- Tabulate COVID-19 Survey answers

Primary Analysis

Patient demographics and baseline clinical characteristics will be summarized by arm, as n (%) and median (interquartile range) for categorical and continuous variables, respectively. To assess any differences in each variable between the two arms, the absolute standardized differences are presented, where a value of 0.2 or less, 0.5, and 0.8 or more correspond to small, medium, and large differences, respectively. Characteristics found to display large differences will be adjusted for in a sensitivity analysis. We will also compare rate of adherence for WFKD after 12 weeks and Med-Plus diets after 12 weeks using a Fisher's Exact test with weekly NDSR (and Cronometer) data. We will develop a composite score to measure a participant's adherence to each diet.

We will use a mixed-effects linear model (1) with HbA1c percent difference from baseline for diet, j, as the outcome. We want to assess for a difference in diet (WFKD vs Med-Plus), while adjusting for fixed effects: order (e.g. study arm), pre-diabetes vs. diabetes status, and a random effect for each participant, i.

$$\left(\frac{HbA1c_{ij}-HbA1c_{i0}}{HbA1c_{i0}}\right) = \beta_o + \beta_1 Order_i + \beta_2 Diabetes_i + \beta_3 Diet_{ij} + \gamma_i$$
(1)

For the primary outcome, we will use a two-sided likelihood ratio test to test for no difference between diet types. The primary analysis will include participants with baseline blood draws, and at least one blood draw in each phase (including crossing over). The primary analysis will be a complete case analysis and use participants' last available lab values in each phase or week 12, if available; patients who did not complete both phases (i.e. crossover) will be excluded. A significance level of 0.05 is set for all analyses. In a sensitivity analysis, we will adjust for baseline weight and percent weight change if weight change from baseline is found to be significant, since this is known to impact HbA1c values; and in a separate analysis, we will adjust for adherence to each diet.

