Similarly, for our secondary outcomes, we will use separate mixed-effects models to evaluate fasting lipids, insulin, glucose, blood pressure and short-chain fatty acids for WFKD vs Med-Plus, adjusting for order, phase, pre-diabetes vs. diabetes status, and repeated measures. A two-sided likelihood ratio test will be used to assess no difference between diet types. For our exploratory outcome comparing diet satisfaction, we will use a Wilcoxon signed-rank test to evaluate the null hypothesis that the difference between pairs follows a symmetric distribution around zero, which indicates similar satisfaction with both diets. We will use a Fisher's Exact test to evaluate any difference in the rate of adherence due to diabetes vs pre-diabetes status, within each diet.

Sensitivity Analysis

Due to COVID-19, visits to collect blood draws were delayed for some participants. These participants report they maintained the phase's diet until the lab measurements could be collected. We will check adherence to diet based on NDSR at Week 12 and Week 12 extra visit (taken when allowed back into clinic), and also check for a change in dietary and exercise habits during shelter-in-place. Potential impact of delays are unclear; subsequently, we will perform a number of sensitivity analyses:

Sensitivity Analysis 1 (SA1): For a simple truncated analysis, we will consider only the first phase (12 weeks) of each group and compare differences (two-sample)

Sensitivity Analysis 2 (SA2): For a simple estimate of Week 12 analysis, we will consider the average of the last lab measurement of each 12 week phase and the extra data point at Week 12 extra visit.

Sensitivity Analysis 3 (SA3): For an extended-phase analysis, we will consider using the last lab measurement from each phase, i.e. the "extra" data timepoints after week 12 in study for some participants.

Sensitivity Analysis 4 (SA4): For a pre-COVID-19 truncated analysis, we will consider the subset of data prior to the official Shelter-in-Place date for the Bay Area, March 16, 2020.

Sensitivity Analysis 5 (SA5): To assess any effect on outcomes due to COVID-19 impact on logistics, we will consider the subset of data when participants received groceries for each diet. We will also evaluate if adherence was better for the first four weeks when groceries were delivered.

Secondary Analysis

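### Adherence by diabetes status is tested only as a yes/no rate with Fisher's exact test, although a composite adherence score is planned; comparing the score would probably be more powerful.

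*SAP*

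**What the plan says.** Under Exploratory outcomes, the SAP lists "Difference in adherence to diet protocols by diabetes vs. pre-diabetes status, according to 3day food records". Nothing there makes adherence a yes/no variable.

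Under Primary Analysis it says: "We will develop a composite score to measure a participant's adherence to each diet". It gives no components, weights or scale for this score. Later in the same section, the test for the exploratory outcome is a "Fisher's Exact test to evaluate any difference in the rate of adherence due to diabetes vs pre-diabetes status", applied separately within each diet.

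On size and error rate: "Forty participants are planned to be randomized between the two arms" and "A significance level of 0.05 is set for all analyses". Diabetes status is a stratification factor ("Randomization will be stratified by diabetes vs pre-diabetes status"), but the expected numbers with diabetes and prediabetes are not given. The SAP states no power for this comparison.

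**The concern.** Fisher's test needs each participant classed as adherent or not. The groups with diabetes and prediabetes are independent, so the test is valid here. The question is whether it is a good choice when a finer measure is already planned. In the same section, satisfaction on a 5-point scale gets a rank-based test, while adherence, which has a score of its own, is tested as two categories without a stated reason.

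Two things are at stake. First, a real difference in how well the two groups follow a diet has less chance of being seen. Second, the result depends on a threshold that the SAP does not state. The SAP is dated 12/18/20 and describes delayed visits and the maintenance phase in the past tense, so some food records probably already existed. It does not say whether anyone had examined them.

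**Working it through.** The SAP has no power figure for this comparison, so there is nothing to reproduce. The check asks how much power the yes/no test gives up.

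**Inputs from the SAP:** at most 40 participants; significance level 0.05; Fisher's exact test within each diet.

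**Assumptions (not in the SAP):** two-sided test; normal, many-valued score; difference d in SD units, 0.8 as central case; split 20/20 or 14/26; threshold set so that 50%, 70% or 80% of all participants are adherent.

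**Step 1: rates implied by a cut.** With group means d/2 above and below the middle and a cut at c, the rates are Φ(d/2 − c) and Φ(−d/2 − c). For d = 0.8 at 20/20, c = 0 gives Φ(0.4) = 66% and Φ(−0.4) = 34%. A cut for 70% overall gives 83% and 57%; for 80%, 90% and 70%.

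**Step 2: Fisher's power.** Sum the probabilities of all pairs of binomial counts for which the two-sided Fisher p-value is at most 0.05.

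As a hand check at the middle cut, the expected counts are about 13 and 7 of 20. One tail of that table is [C(20,13)² + C(20,14)² + C(20,15)² + …] / C(40,20) = 0.0436 + 0.0109 + 0.0017 + 0.0002 = 0.0564, so the two-sided p is 0.113. The typical table is not significant. At 14 and 6, p = 2 × (0.0109 + 0.0017 + 0.0002) = 0.026.

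**Step 3: power on the score.** The t test has non-centrality d√(n₁n₂/(n₁+n₂)). At 20/20 this is 0.8 × √10 = 2.53, giving 69%. At 14/26 it is 0.8 × √9.1 = 2.41, giving 65%. Rank-sum power is simulated: about 66% (repeat runs 66-67%) and about 61% (repeat runs 61-63%).

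**Results for d = 0.8**

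| Split | Fisher, 50% adherent | 70% | 80% | Rank-sum on score |
|---|---|---|---|---|
| 20/20 | 36% | 35% | 27% | about 66% |
| 14/26, smaller group adheres better | 41% | 28% | 15% | about 61% |
| 14/26, larger group adheres better | 41% | 42% | 40% | about 61% |

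**Step 4: where the loss arises (20/20, d = 0.8, middle cut).** The t test on the score has 69%, an uncorrected two-proportion test about 50%, and Fisher 36%. Both the cut and Fisher's conservatism contribute. Fisher's true size is 2.0-2.5% at 20/20 and 3.1-3.6% at 14/26, against the nominal 5%.

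**Step 5: other effect sizes (20/20, middle cut), Fisher vs t test.** d = 0.5: 14% vs 34%. d = 1.0: 55% vs 87%. d = 1.2: 73% vs 96%. d = 1.5: 91% vs nearly 100%. The relative loss shrinks as the effect grows.

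**The case against.** The case for leaving the plan as it is has several parts.

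- **The outcome is exploratory and the test is valid.** With a fixed threshold, Fisher's test does not inflate type I error, and a proportion is easy to interpret. This stands and keeps the point minor.
- **The rate need not be the score cut in two.** A reader might infer that the score must be dichotomised at a point chosen after the food records are in. The SAP does not say so. It mentions the rate and the score in separate sentences, and the rate could come from meeting diet targets. The Background section gives a carbohydrate ceiling of 50 grams per day for the ketogenic diet, though it is not named as the adherence criterion and Med-Plus has no numeric counterpart there. A definition may also sit in the protocol, which is not at hand. What stands is that this SAP gives no threshold for the rate it tests.
- **The score is undefined too.** Moving to a rank test without defining the score would replace one open choice with another. This stands, and the fix covers it.
- **The score would not rescue a moderate effect.** At 20/20 and d = 0.5, even the t test has only 34% power. True, and the reason the interval matters more than the p-value.
- **The SAP does not say that a non-significant result will be read as similar adherence.** Correct. That is a risk in interpretation, not something the plan states.

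**Conclusion.** The point holds as a minor, inexpensive improvement: the SAP plans a finer adherence measure but tests the outcome only as a rate, with a conservative test and no stated threshold. For a normal, many-valued score and a 0.8 SD difference, Fisher's power is 27-36% against about 66% at 20/20. At 14/26 it is 15-42% against about 61%, depending on the cut and on which group adheres better.

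A reader might infer that the test simply halves the power. The SAP does not support that as a general statement, because it gives no split, effect size or score scale. The ratio of Fisher to rank-sum power runs from 15/61 = 0.25 to 42/61 = 0.69 in the 14/26 cases alone. The loss is smaller for very large effects or a coarse score. Nor does a yes/no cut discard most of the information: a median cut of a normal score keeps about 2/π = 64% efficiency, so a substantial part is the accurate description. The test of diet on HbA1c does not use this comparison.

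**What to change.** 1. Define the composite adherence score (components, weights and scale) before any adherence data are analysed.
2. Within each diet, compare the score between participants with diabetes and prediabetes using a Wilcoxon rank-sum test. Report the estimated difference with its 95% confidence interval.
3. Keep percent adherent as description only, with its threshold also fixed beforehand.

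This needs no new data or visits. The cost is some extra specification work, mainly in defining the score, and a measure that is less directly interpretable than a proportion. Reporting percent adherent alongside makes up for part of that.

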For our secondary analysis, we want to investigate: (a) a potential difference in the primary outcome by diabetes status; (b) the different trajectories of each diet; and (c) different metrics using continuous glucose monitoring data and how that compares with the gold standard HbA1c data. In a low-power analysis for (a), we will use model (1) and include an interaction term for diet and diabetes status. For (b), we will use all time points in a model similar to (1) but with a time variable. Lastly for our analysis in (c), we will consider different metrics used in the literature for continuous glucose monitoring and compare trajectories of each metric with that of the gold standard using HbA1c data.

Exploratory Analysis

For our exploratory analysis, we want to investigate long term maintenance. Upon completing both diet phases, for three months participants were instructed to eat the diet of their choosing. This analysis will be largely descriptive on what participants were consuming and their change in lab measurements.

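### Sensitivity Analysis 1 reads as an unadjusted two-sample test that omits the diabetes stratum used in randomisation and in model (1); if that stratum is prognostic, its interval is too wide

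*SAP*

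**What the plan says.** Under Study Design, the SAP states: "Randomization will be stratified by diabetes vs pre-diabetes status". The Primary Analysis section then keeps that factor in its models:

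- Model (1), for HbA1c percent change, is fitted "adjusting for fixed effects: order (e.g. study arm), pre-diabetes vs. diabetes status, and a random effect for each participant, i".
- The secondary-outcome models are fitted "adjusting for order, phase, pre-diabetes vs. diabetes status, and repeated measures".

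The Secondary Analysis section builds on model (1). For part (a), "we will use model (1) and include an interaction term for diet and diabetes status"; for part (b), "we will use all time points in a model similar to (1) but with a time variable".

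The Sensitivity Analysis section lists five analyses prompted by COVID-19 delays. SA1 is introduced as a simple truncated analysis: "we will consider only the first phase (12 weeks) of each group and compare differences (two-sample"). It names no covariate and does not refer to model (1), and nothing elsewhere says that the sensitivity analyses inherit model (1)'s terms. SA2 to SA5 describe changes in the data used and name no statistical method, so nothing is claimed about them here.

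**The concern.** Of the five sensitivity analyses, SA1 is the one described as a comparison between two groups of different people. In the crossover comparison each person is their own control, so a factor fixed within a person matters little to the diet contrast. In SA1 it can matter.

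Stratified allocation balances diabetes status across arms, which removes stratum differences from the diet estimate. A plain two-sample test does not know this and still counts those differences as noise. Its standard error then overstates the real uncertainty, its interval over-covers and its test is conservative.

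What is at stake is how SA1 can be read. It is meant to help show whether the result survives the disruption to visits. If it differs from the primary analysis in adjustment as well as in data, an SA1 interval that crosses zero is harder to interpret, and avoidable conservatism makes such an interval more likely.

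**Working it through.** The SAP gives no power, SD, effect size or stratum share for SA1, so there is no figure of its own to reproduce.

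**Inputs from the SAP.** Sample size: "Forty participants are planned to be randomized between the two arms". Level: "A significance level of 0.05 is set for all analyses". A two-sided test is stated for the primary outcome.

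**Assumptions.** 1:1 allocation (20 per arm); two-sided testing in SA1; strata of 10/10 in each arm; normal errors with within-stratum SD 1; a stratum gap *g* in mean percent change, in within-stratum SDs; true diet effect 0.8 SD for power.

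**Step 1: what model (1) becomes in phase I.** Order and diet coincide, so one drops out. There is one value per person, so the participant random effect cannot be separated from the residual. What remains is a linear model on diet and diabetes status.

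**Step 2: the estimate.** With balanced strata the stratum effect cancels from the difference in arm means. Both analyses give the same point estimate (largest simulated gap below 1e-14). Its true SE is sqrt(1/20 + 1/20) = 0.316, whatever *g* is.

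**Step 3: the unadjusted residual.** Within each arm, people lie *g*/2 either side of the arm mean, which adds 40 × *g*²/4 to a residual sum of squares on 38 df. The residual SD is therefore inflated by about sqrt(1 + (40*g*²/4)/38):

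- *g* = 0.5: sqrt(1 + 2.5/38) = 1.032
- *g* = 1: sqrt(1 + 10/38) = 1.124

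The share of variance explained by the stratum is (*g*²/4)/(1 + *g*²/4): 0.0625/1.0625 = 6% and 0.25/1.25 = 20%.

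**Step 4: simulation**, 320,000 runs per setting, two-sample t test against a linear model on diet and stratum:

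| Gap *g* | Type I error, unadjusted | Type I error, adjusted | Power, unadjusted | Power, adjusted | Interval width, adjusted/unadjusted |
|---|---|---|---|---|---|
| 0 | 5.0% | 5.0% | 69% | 69% | 1.0007 |
| 0.5 SD | 4.3% | 5.0% | 67% | 69% | 0.969 |
| 1 SD | 2.8% | 5.0% | 60% | 69% | 0.890 |

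At *g* = 1 the mean unadjusted SE is 0.353 and the mean adjusted SE 0.314, against the true 0.316. The width ratios agree with step 3: 1/1.032 = 0.969 and 1/1.124 = 0.890. A noncentral t calculation with 37 df gives adjusted power of 69.3% at 0.8 SD.

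**Step 5: other assumptions.**

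- *Effect 0.6 SD*: power 43% vs 46% at *g* = 0.5, and 36% vs 45% at *g* = 1 (unadjusted first).
- *Effect 1.0 SD*: 85% vs 87%, and 81% vs 87%.
- *Strata 6/14 in each arm*: type I error of the unadjusted test 4.4% and 3.1%; power 67% and 62%, against 69% adjusted.
- *8 of 40 lost at random*, which unbalances the strata: type I error 4.5% and 3.3%; power 56% vs 59%, and 49% vs 59%.

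A separate simulation of 40,000 trials per setting gave unadjusted intervals 3.1% wider at *g* = 0.5, 12.4% wider at *g* = 1 and no wider at *g* = 0. The 12.4% is the same quantity as the 11% narrowing: 1/0.890 = 1.124.

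**The case against.** The strongest case against is that the unadjusted reading is inferred. SA1 never says it is unadjusted. The five entries are one-line descriptions of which data to use, and the word two-sample may mean only that the contrast is now between people; a model on diet plus stratum also compares two independent samples. On this view SA1 is under-described, not wrong. That stands as far as it goes: the text does not settle the matter. But SA1 is the only one of the five that names a method of comparison, calls itself simple and points to no model, so an analyst following it literally would run an unadjusted test.

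Second, even then the test is valid, unbiased and not tied to any decision rule, and the point estimate is unchanged under balance. All true, and the reason the point is minor.

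Third, the size rests on figures the SAP does not supply. The outcome is already scaled by each person's baseline HbA1c, and nothing in the document supports a 1 SD gap between strata. This also stands: the 1 SD row is an illustration of a strong stratum, and the loss may be small or zero. The plan does, however, choose this factor for stratification, for the primary model and for an interaction test.

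Last, SA1 names no outcome, and it does not say whether the primary analysis's exclusion of people who did not complete both phases applies. Those gaps are real but separate, and adding the stratum term does not close the second.

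**Conclusion.** The concern holds in its conditional form. SA1 reads as an unadjusted comparison after stratified randomisation, and if diabetes status predicts percent change in HbA1c, its interval is wider than it need be and its test conservative. There is no bias and no inflated false-positive rate, and the primary test is unaffected.

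Under the assumptions above, the loss is nil with no stratum gap, 2 points of power at 0.5 SD and 9 points at 1 SD. Which of these applies cannot be told from the SAP. Adjustment does not make SA1 a strong test either: even with the stratum in the model, about 3 in 10 true effects of 0.8 SD would be missed with 20 per arm. The point is minor, and confidence is medium because the wording of SA1 allows more than one reading.

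**What to change.** Replace the description of SA1 with one sentence: model (1) restricted to phase I, that is, a linear model of first-phase HbA1c percent change on diet and diabetes/pre-diabetes status, with order omitted because it coincides with diet in that phase. The same sentence could usefully say who is included.

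No new data are needed, and the cost is one degree of freedom. If the stratum is not prognostic, the interval is about 0.1% wider with 40 analysed, or about 0.5% wider (0.3 points of power) if 8 of 40 are missing at random.

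### Trajectory analysis (b) carries a participant-only random effect over to two visits per diet; if same-phase values correlate, a diet test is too liberal and the diet-by-time test too conservative

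*SAP*

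**What the plan says.** Model (1), under Primary Analysis in the SAP, has fixed effects for order, diabetes status and diet, and "a random effect for each participant, i". No other random term and no residual correlation structure is given. Its outcome is one percent difference from baseline per diet per participant.

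Under Secondary Analysis, item "b) the different trajectories of each diet" is to be studied as follows: "we will use all time points in a model similar to (1) but with a time variable". The time variable is the only stated change. The form of time, the covariance and the contrast to be tested are not given.

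The Study Design section puts the measurements at "weeks 0, 6, 12, (Phase I, weeks 1-12), 18, 24 (Phase II, weeks 13-24) and 36 (Maintenance Phase", so each participant has two visits on each diet. The general rule for error control is "A significance level of 0.05 is set for all analyses".

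**The concern.** With one value per diet, a participant intercept describes all the within-participant correlation there is to describe. With two values per diet it imposes a restriction: weeks 6 and 12 on one diet are assumed to be exactly as correlated as week 6 on one diet and week 24 on the other.

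That fails if participants differ in their response to a diet, or if successive HbA1c values are serially correlated. The SAP itself gives reasons to expect the first. Its Background speaks of effects that differ between populations, analysis (a) looks for a diet-by-diabetes interaction, and a sensitivity analysis adjusts for adherence to each diet. Adherence that varies by person and by diet makes two visits on the same diet more alike. The baseline shared by all of a participant's percent changes does not remove this, because the participant intercept absorbs it.

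Two error bars are at stake. The second visit of a phase would count as largely new information about the diet, so the standard error of a diet difference would be too small. Stable person-by-diet differences would enter the residual variance, so the standard error of change within a phase, which is the trajectory, would be too large.

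**Working it through.** **Inputs.** From the SAP: a two-sided 0.05 level; 40 participants; four on-diet visits (weeks 6, 12, 18, 24); a participant intercept as the only stated random term. Assumed: 20 participants per order; complete data; and rho, the correlation of the two same-phase residuals after the participant effect. The SAP gives no correlation or variance, so rho is varied.

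**Diet contrast.** Take unit residual variance, correlation rho within a phase and 0 across phases.

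- True variance of (phase 1 mean − phase 2 mean) = (1+rho)/2 + (1+rho)/2 = 1+rho.
- Each participant has three within-participant degrees of freedom: one between phases with variance 1+rho, and two within phases with variance 1−rho. The random-intercept model pools them: [(1+rho) + 2(1−rho)]/3 = 1−rho/3. It reports this as the variance of the diet contrast.
- Ratio of true to reported variance: VR = (1+rho)/(1−rho/3).
- Size of the nominal 5% test: 2Φ(−1.96/√VR).

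**Within-phase change and diet-by-time.**

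- True variance of a within-phase change = 2(1−rho); reported = 2(1−rho/3).
- Reported over true standard error: k = √[(1−rho/3)/(1−rho)].
- Size of the diet-by-time test: 2Φ(−1.96k).

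**Check against the plan's own level.** At rho = 0, VR = 1 and k = 1, and both tests return 5.0%.

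**Results (closed form).**

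| rho | VR | diet SE too small by | diet test size | within-phase SE too large by | diet-by-time test size |
|---|---|---|---|---|---|
| 0.1 | 1.14 | 6% | 6.6% | 4% | 4.2% |
| 0.2 | 1.29 | 12% | 8.4% | 8% | 3.4% |
| 0.3 | 1.44 | 17% | 10.3% | 13% | 2.6% |
| 0.5 | 1.80 | 25% | 14.4% | 29% | 1.1% |
| 0.7 | 2.22 | 33% | 18.8% | 60% | 0.2% |

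Example at rho = 0.5: VR = 1.5/0.8333 = 1.80 and 1.96/√1.80 = 1.461, so the two-sided size is 14.4%. Also k = √(0.8333/0.5) = 1.291 and 1.96 × 1.291 = 2.530, so the size is 1.1%.

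**Simulation.** 20,000 trials per setting, 40 participants, likelihood ratio test, with time entered as linear, within-phase or categorical. The fits used within-participant contrasts, which are equivalent to a random-intercept fit in balanced data. Ranges are over the three forms of time.

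| setting | diet test | diet-by-time test |
|---|---|---|
| rho 0 | 5.1–5.4% | 5.5–5.6% |
| rho 0.1 | 6.3–7.5% | 4.4–4.7% |
| rho 0.2 | 8.6–9.0% | 3.7–4.3% |
| rho 0.5 | 14.6–15.6% | 1.3–2.4% |
| rho 0.7 | 19.0–19.8% | 0.3–1.2% |
| AR(1) 0.1 | 6.1–6.4% | 4.9–5.8% |
| AR(1) 0.7 | 12.8–13.0% | 1.9–3.1% |

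A joint two-degree-of-freedom test of diet and diet-by-time gave 6.7–7.0%, 9.1–10.5% and 11.5–13.3% at rho 0.2, 0.5 and 0.7.

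**Power for the trajectory.** Suppose a contrast has 80% power with the correct standard error, so that its standardised effect is 1.96 + 0.842 = 2.802. Power under the participant-only model is then Φ(2.802 − 1.96k): about 75%, 61% and 37% at rho 0.2, 0.5 and 0.7.

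**With a participant-by-phase effect.** For rho 0, 0.2, 0.5 and 0.7 the diet test returns to 5.7–5.8% with a likelihood ratio test and 4.9–5.0% with an F test.

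**The case against.** The strongest reply is that the SAP does not spell out the model for (b). It says the model resembles (1), whereas for (a) it says model (1) itself is used with an added interaction. The paragraph on the other secondary outcomes mentions phase and repeated measures. So the participant-only structure is inferred. This stands as a caution. But the one change named is a time variable, so participant-only is the plain reading, and stating the structure is the remedy either way.

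A reader might go further and infer that the diet comparison in (b) will run at 8 to 19%. The documents do not support that as a fact, for three reasons:

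- The figure depends on rho, which the SAP does not give. Size is 5.0% at rho = 0, and lower under AR(1) than under the same value of rho for all correlations of 0.3 or more that were tried.
- No diet main-effect test is named for (b). The sentence "we will use a two-sided likelihood ratio test to test for no difference between diet types" belongs to the primary outcome. The stated aim of (b) is trajectories, for which the error runs the other way: lost power rather than false positives.
- Same-diet visits are not treated as independent. The participant intercept correlates them; they are independent only given that intercept. The restriction is equal correlation for same-diet and cross-diet pairs.

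It is also fair that the calculation uses four balanced on-diet visits. Baseline, week 0, week 36 and the extra visits after COVID-19 delays also exist, and using them would change the exact figures.

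**Conclusion.** The concern holds in conditional form. As written, (b) leaves out any extra likeness between two visits on the same diet. If that likeness is positive, both error bars are wrong, in opposite directions. For an assumed rho of 0.1 to 0.7, a diet main-effect test in (b) would run at about 7 to 19% (about 6 to 13% under AR(1) of 0.1 to 0.7). For rho of 0.2 to 0.7 the within-phase standard error would be about 8 to 60% too large, and the diet-by-time test would run at about 3.4% down to 0.2%.

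These figures rest on the assumed correlation, on four complete on-diet visits and on the plain reading of the model. The primary analysis has one value per diet and is not touched. This is a secondary analysis with no decision attached to it, but the 0.05 level is set for all analyses and the repair is small, so it should be made.

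**What to change.** In Secondary Analysis (b), state that the model has a participant random effect plus a participant-by-phase random effect. The alternative is an unstructured covariance over weeks 6, 12, 18 and 24 in place of both, which also accommodates serial decay. Name the contrast to be tested: diet-by-time, and diet as well if it is to be tested. A small-sample degrees-of-freedom correction is an optional refinement, since the likelihood ratio test with the added term already runs at 5.7–5.8%.

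The cost is a line or two of wording and no new data. Any diet main effect in (b) gets a wider interval when rho is positive. The participant-by-phase term adds one variance parameter. The unstructured option has 4 × 5/2 = 10 covariance parameters against two in the random-intercept model, which is a good deal to estimate from about 40 participants, so the participant-by-phase term is the lighter choice.
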